13.2 Randomization/Stratification

We aim to enroll 24 ER+ participants and 12 ER- participants for a total of 36 participants. As this is a non-randomized trial, stratification for randomization is not applicable. One of the analyses to be performed will be stratified by estrogen receptor status.

13.3 Accrual and Feasibility

According to Dowsett et al., there was a mean decrease in Ki67 of 59.5% and an estimated standard deviation (SD) of 57.5% with tamoxifen, the least effective among tamoxifen alone, anastrozole alone, and tamoxifen/anastrozole combination.³⁴ As we do not know if 9cUAB30 will have as much of a decrease as tamoxifen, we will use a range of more conservative estimates, from 50-75% of 59.5%, or 29.8-44.6%. According to Chen et al., there was a mean increase in Ki67 of 1.7% with a SD of 7.6% based on three untreated observations with the time interval comparable to the proposed study.⁴³ However, three observations for estimation of SD is not reliable. Instead we used the widest interval-based SD estimate of 14.8% (from the 2-4 day interval), to be conservative. We also conservatively used an estimate of 0% for change in the control group instead of 1.7%, again, because of the sample size consideration.

Since we are using matched pairs, we needed to estimate the mean and SD of the difference between the matched pair. With 0% as our control estimate, the estimate of the range of the mean difference is thus 29.8-44.6%. The SD is estimated using the equation $\sqrt{\sigma_T^2 + \sigma_C^2 - 2\rho\sigma_T\sigma_C}$ where σ_T is the SD of the treatment group, σ_C is the SD of the control group, and ρ is the correlation between the matched pair. The value of this equation increases as ρ decreases in value, so an estimate using a smaller correlation coefficient is more conservative. This correlation is unlikely to be negative. Also, if the effect on Ki67 is not dependent on the factors that will be used to choose the matched controls, the correlation is likely to be close to 0. For these reasons, we use 0 as the estimate of ρ ; this gives an estimate of 59.4% for the SD of the difference between the matched pair.

We will enroll 36 participants, and obtain 36 matched pairs. Stratified analyses will be conducted if we reach a minimum of 12 participants (and matched pairs) with ER-. Assuming 20% of the participants cannot be evaluated at the end of study due to dropout or unevaluable/unavailable specimen, we will have approximately 28 participants, with 9 participants with ER- and 19 with ER+. The range of mean difference

in the change of 29.8-44.6% and the estimated SD of 59.4% result in an effect size ranging from 0.502-0.751. The table below shows the attainable power of a one-tailed level 0.05 paired test under various effect sizes. With 32 participants, the study will have 0.82-0.98 power to detect the range of effect size of 0.502-0.751. With the 9 participants and matched controls in the ER- group, there will be a power of 0.39-0.65 to detect an effect size range of 0.502 -0.751 between the treatment group and the matched controls. With the 19 participants and matched controls in the ER+ group there will be a power of 0.67-0.93 to detect the same effect size range. Because of the nature of the study being exploratory, we are not making adjustment for multiplicity of testing in subgroups defined by ER status.

Effect Size	Subgroup		
	All (n=28)	ER+ (n=19)	ER- (n=9)
0.751	0.98	0.93	0.65
0.626	0.94	0.83	0.52
0.502	0.82	0.67	0.39

Power for Different Estimated Effect Sizes

13.4 Primary Objective, Endpoint(s), Analysis Plan

The primary objective will be to evaluate if there is a significant decrease in proliferation (Ki67) expression in breast cancer cells from baseline to post-exposure in participants treated with 9cUAB30 compared with matched controls. The primary endpoint is the absolute change from baseline to post-exposure in 9cUAB30 treated and matched controls in Ki-67 in breast epithelial cells obtained by needle core biopsy. The baseline, post-exposure, absolute change in Ki-67, and difference in absolute change between the treated and matched controls will all be summarized with descriptive statistics. The primary analysis will compare the absolute change in Ki-67 between treatment and matched “control” group using a one-tailed paired t-test or Wilcoxon signed-rank test, as appropriate, at a significance level of 0.05.

13.5 Secondary Objectives, Endpoints, Analysis Plans

The first of secondary objectives is to evaluate if there is a difference in the change in apoptosis (caspase 3) from baseline to post-exposure in breast cancer epithelial cells in participants treated with 9cUAB30 compared with matched controls. In the second of secondary objectives, we will examine the differences in gene expression from baseline to post-exposure breast cancer samples using a custom gene panel from Nanostring Technologies. Examined genes will be selected as described below and will include 23 genes. Prospective biomarkers on the panel will include (A) biomarkers associated with cell proliferation or apoptosis: PCNA, p21, p27, caspase 3; (B) potential biomarkers of rexinoid activity reported in published studies: ABCA1, ABCG1, RAR β , SREBP-1c, cyclin D1, IGFBP6; (C) potential biomarkers of response to 9cUAB30 as defined in our preliminary studies: RET, MEN1, mTOR, AKT1, AKT2, 4EBP1, eIF4G1, S6K, IGFBP5, TGF β R1, PPAR α , PPAR γ ; and (D) housekeeping genes for normalization: GAPDH, TUBB, PGK1, GUSB, and CLTC. Additionally, as possible, we will perform IHC for a subset of 5 of the most differentially regulated genes found on Nanostring to verify that gene expression data also results in protein differences.

One of the secondary objectives will be to examine if the Cmax at day 1 is increased from 957 ng/ml by reducing the number of capsules for the 240 mg dose level. The endpoint for this objective is Cmax measured at day 1. This will be tested using a one-tailed one-sample Student t-test.

Observed toxicities seen in this study will be compared with those known to occur from retinoid use. This comparison will be qualitative by necessity and descriptive in nature. As such these will be described in descriptive statistics.

13.6 Reporting and Exclusions

All participants who receive any 9cUAB30 will be analyzed for adverse events. Subjects that maintain 90% compliance for the time period beginning day 1 and ending on the day before surgical intervention will be considered compliant. Compliance will be measured through pill counts conducted by the study coordinator and recorded in the CRF. For biomarker modulation, all participants that have evaluable pre- and post-treatment samples will be included in the analysis. Compliance and availability of evaluable samples for biomarker studies will be included in descriptive statistics.

13.7 Evaluation of Toxicity

All participants will be evaluable for toxicity from the time of their first dose of 9cUAB30. The toxicity will be tabulated by severity with descriptive statistics.

13.8 Evaluation of Response

All participants included in the study will be assessed for response to intervention with 9cUAB30, specifically decrease in proliferation and increase in apoptosis. All of the participants who met the eligibility criteria will be included in the main analysis. All conclusions regarding efficacy will be based on all eligible participants.

13.9 Interim Analysis

There is no planned interim analysis of the primary endpoint of the study. Safety data will be monitored by the consortium's data monitoring committee.

There will be an interim analysis after first 5 participants complete the study at dose 240 mg. This will be to analyze the Cmax and evaluate toxicity data collected for the first 5 participants.

The dose of the study will be reduced to 160 mg if one of the following criteria is met:

1. If the mean Cmax is not >957 ng/mL
2. If ≥ 2 subjects experience grade 2 hypertriglyceridemia of any attribution

If the study dose is reduced to 160mg due to the toxicity criteria at 240mg, then another cohort of 5participants will be evaluated only for toxicity.

If any subjects experience grade 4 or higher toxicity, the study will be suspended for accrual. The study chair will consult with the DSMC for study termination or other course of action. The PI will work with the NCI DCP Investigators to make a decision in consideration of the DSMC's recommendation.

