5.6 Dose Modification

No dose modifications will occur for an individual participant. The study dose may be reduced from 240 mg/day to 160 mg/day if interim dose modification rules are met (see Section 13.9). No other dose modifications will be allowed.

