13. STATISTICAL CONSIDERATIONS

13.1 Study Design/Description

We aim to enroll 24 ER+ participants and 12 ER- participants for a total of 36 participants. We plan to “pilot” the 240 mg dose in 5 initial participants with planned assessment of Cmax (Tmax usually at 2 hours) at 2 hours post initial dose (see section 2.3 for further information). In the original 9cUAB30 Phase I study, we saw a flattening of the otherwise linear PK concentration curve; there was a mean Cmax of 957 ng/ml (SD 611) at the 240 mg dose level, similar to the mean Cmax of 983 (SD 434) for the 160 mg dose level. If Cmax had continued to be linear, we will have expected to see a Cmax of 1668 at the 240 mg dose level (calculated using linear regression with a forced intercept of 0, omitting the 240 mg level). We will test the hypothesis H_0 : Cmax=957 (concentration curve is flat) vs the hypothesis H_A :Cmax=1668 (concentration curve is linear) with a one-tailed one-sample Student t-test. Assuming a standard deviation of 611, we will have 0.69 power to reject H_0 : Cmax=957 given that the true mean Cmax is 1668 using a one-tailed one-sample t-test of level 0.05. Based on the results of this analysis, if we do not reject H_0 and the dose gets changed to 160 mg after enrolling 5 participants, 36 additional participants will be enrolled to meet total of 36 participants for data analysis on 160 mg dose and 41 participants total in the study. If we reject H_0 we

will continue at 240 mg/day and enroll 31 more subjects.

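### Section 13.9 sets the dose by comparing the mean Cmax with 957 ng/mL, while section 13.1 sets it by a t-test; read literally, 13.9 does not have the stated 0.05 level and 0.69 power

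*Combined protocol and SAP*

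**What the plan says.** Section 13.1 sets up a one-tailed one-sample t-test at level 0.05 of a mean Cmax of 957 ng/mL (flat curve) against 1668 ng/mL (linear curve). It assumes an SD of 611 and says "we will have 0.69 power to reject" the null at 1668. It ties the dose to the result. For non-rejection it reads "Based on the results of this analysis, if we do not reject" the null "and the dose gets changed to 160 mg after enrolling 5 participants, 36 additional participants will be enrolled"; on rejection the trial "will continue at 240 mg/day and enroll 31 more subjects". Section 13.5 poses the same question as a secondary objective, to "examine if the Cmax at day 1 is increased from 957 ng/ml", and adds "This will be tested using a one-tailed one-sample Student t-test".

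Section 13.9 lists two triggers for reducing to 160 mg. One is hypertriglyceridemia. The other is "If the mean Cmax is not >957 ng/mL". It gives no test, level or confidence bound, and does not refer to 13.1.

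The operational sections point to 13.9. Section 3 refers to it for the continue-or-reduce decision. Section 5.6 states "The study dose may be reduced from 240 mg/day to 160 mg/day if interim dose modification rules are met (see Section 13.9" and then rules out any further change of dose. Section 2.3 asks for a significant rise over 957 in order to continue, but then describes the opposite case as levels not appreciably above 957. The Schema speaks of establishing a Cmax above 957.

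**The concern.** One dose decision has two PK rules. A reader who follows the cross-references reaches a comparison of the mean with 957 and may never meet the t-test. Any mean above 957 that is not significantly above it continues at 240 mg under 13.9 and drops to 160 mg under 13.1.

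The pilot exists because 240 mg gave no higher Cmax than 160 mg in the Phase I study (means 957 and 983 in section 13.1). The decision fixes the dose for every later participant. It also fixes whether 31 or 36 more are enrolled, since the five pilot participants count toward the 36 only if 240 mg continues. The error rates quoted for it belong to the t-test alone. Where the rules differ, the choice between them is left open after the data are seen.

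**Working it through.** **Inputs, all from section 13.1:** n = 5; SD = 611; null mean 957; alternative mean 1668; one-tailed level 0.05; Phase I mean at 160 mg, 983. The PK criterion is taken alone, with normal data.

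**Step 1: reproduce the stated power.** Standard error = 611/√5 = 273.2. Noncentrality = (1668 − 957)/273.2 = 2.602. With 4 degrees of freedom the one-sided critical value is 2.132. The noncentral t distribution gives power 0.689, which matches the stated 0.69. A two-sided t-test would give 0.507 and a one-sided z-test 0.831, so 0.69 is the power of the one-tailed t-test and of neither alternative.

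**Step 2: the literal 13.9 rule.** The trial continues if the mean of five values exceeds 957, so P(continue) = Φ((μ − 957)/273.2).

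**Step 3: compare.** The t-test cannot reject when the sample mean is 957 or less, so every rejection is also a continuation under 13.9. The probability that the rules disagree is therefore the simple difference. The share of 13.9 continuations that 13.1 would reduce is 1 − P(reject)/P(mean > 957).

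| True mean Cmax | Continue, 13.1 t-test | Continue, literal 13.9 | Rules disagree | Share of 13.9 continuations that 13.1 would reduce |
|---|---|---|---|---|
| 957 (flat) | 0.050 | 0.500 | 0.450 | 0.90 |
| 983 (160 mg mean) | 0.059 | 0.538 | 0.479 | 0.89 |
| 1312 (midway) | 0.288 | 0.903 | 0.615 | 0.68 |
| 1668 (linear) | 0.689 | 0.995 | 0.306 | 0.31 |

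Disagreement peaks at 0.632, at a true mean of about 1233. A simulation of 1,000,000 samples per mean gave disagreement of 0.451, 0.479, 0.617 and 0.306 for the four rows. It produced no rejection with a mean at or below 957.

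**Step 4: the zone of conflict.** With an observed SD of 611, the t-test needs a mean above 957 + 2.132 × 273.2 ≈ 1540 ng/mL. Any mean above 957 and up to about 1540 gives 240 mg under 13.9 and 160 mg under 13.1.

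**Step 5: sensitivity.** The 0.50 at a true mean of 957 does not depend on the SD, but it does assume a symmetric distribution. With lognormal data of the same mean and SD, the literal rule continues with probability 0.44 at 957 and above 0.999 at 1668; the t-test gives 0.013 and 0.770. With normal data, changing the SD to 434 or 800 moves the literal rule at 1668 to above 0.999 or to 0.977.

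**The case against.** The strongest reply is that the sections can be reconciled. Section 13.9 says the dose falls if a criterion is met; it does not say only if. Because the t-test never rejects at a mean of 957 or below, the 13.9 trigger lies inside the 13.1 rule, and a reader who obeys both always reaches the 13.1 decision. The mean Cmax in 13.9 can also be read as the parameter under test, which makes the criterion shorthand for the test's conclusion. Section 13.5, the first statement in 2.3 and the Schema all lean that way. The closing sentence of 5.6 may exclude other kinds of dose change rather than exclude 13.1.

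These readings are possible, and the t-test is the better-supported intent. If either reading is adopted, the disagreement is zero. But 13.9 does not refer to 13.1, nothing marks its criterion as partial or abbreviated, and sections 5.1, 5.2 and 5.6 make reduction depend on the interim dose modification rules being met. The literal reading is a natural one.

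Two points limit the consequences. The Ki-67 test's error rate is unaffected, and the hypertriglyceridemia and grade 4 rules apply either way. Section 6.2 also considers doses up to 240 mg/day for up to 28 days safe. On timing, the protocol is Version 20 of January 2022, so the interim has probably passed, though the documents do not report it. If it has, rewording changes no past decision, but readers still need to know which rule was used.

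**Conclusion.** The concern holds. As written, 13.9 is a decision threshold that does not deliver the level and power stated in 13.1. On the literal reading, a flat curve is carried forward at 240 mg with probability 0.50 instead of 0.05, and a linear one with probability 0.995 instead of 0.69. The rules give different doses in 31% to 63% of trials for true means from 957 to 1668. These figures rest on the literal reading (continue unless a listed criterion is met), the PK criterion alone, n = 5, SD 611 and normal data. A lognormal distribution lowers the 0.50 to 0.44, which is still far from 0.05. This should be fixed: the rule sets the dose for all later participants and the number still to enroll.

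**What to change.** Replace the first criterion in 13.9 with: reduce if the one-tailed 0.05 one-sample t-test of section 13.1 does not reject Cmax = 957 ng/mL. Use the same wording in the Schema and section 2.3. The stated 0.05 and 0.69 then describe the rule actually in force.

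If the sponsor used, or intends, the sample-mean rule, correct 13.1 instead and state 0.50 and 0.995 in place of 0.05 and 0.69.

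If the interim has already taken place, report which rule was applied, with the observed mean, SD and test result.

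The cost is one line in 13.9 and matching wording in two other places, with no new samples, visits or participants.

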Primary: Change in proliferation (Ki-67)

Secondary:

- Change in apoptosis (Cleaved Caspase 3)
- Differences in gene expression from pre and post treatment samples using a custom gene panel from Nanostring Technologies
- Examine Safety and PK drug levels in first 5 participants for interim analysis
- PK drug levels
- Increase gene expression of type I immune cells in the tumor immune environment
- Examine safety in comparison to known Retinoid toxicity

Exploratory: Increase activated type I dendritic cells in peripheral blood (participants 6-25)

*If the interim analysis for dose 240mg does not establish Cmax >957 ng/mL or has ≥ 2 subjects experience grade 2 hypertriglyceridemia of any attribution then the study dose will be changed to 160mg.

TABLE OF CONTENTS

SCHEMA.....	4
1. OBJECTIVES	7
1.1 Primary Objective.....	7
1.2 Secondary Objectives	7
1.3 Exploratory Objective.....	7
2. BACKGROUND.....	8
2.1 Study Disease	8
2.2 Study Agent	8
2.3 Rationale.....	11
3. SUMMARY OF STUDY PLAN	13
4. PARTICIPANT SELECTION	15
4.1 Inclusion Criteria	15
4.2 Exclusion Criteria	16
4.3 Inclusion of Women and Minorities	17
4.4 Recruitment and Retention Plan	17
5. AGENT ADMINISTRATION.....	18
5.1 Dose Regimen and Dose Groups	18
5.2 9cUAB30 Administration	18
5.3 Run-in Procedures	18
5.4 Contraindications.....	18
5.5 Concomitant Medications	19
5.6 Dose Modification	19
5.7 Adherence/Compliance.....	19
6. PHARMACEUTICAL INFORMATION.....	19
6.1 9cUAB30 (IND 101,064, NCI, DCP)	19
6.2 Reported Adverse Events and Potential Risks	20
6.3 Availability	24
6.4 Agent Distribution	24
6.5 Agent Accountability.....	24
6.6 Packaging and Labeling.....	25
6.7 Storage	25
6.8 Registration/Randomization	25
6.9 Blinding and Unblinding Methods.....	25
6.10 Agent Destruction/Disposal.....	25
7. CLINICAL EVALUATIONS AND PROCEDURES	26
7.1 Schedule of Events	26
7.2 Baseline Testing/Prestudy Evaluation	27
7.3 Evaluation During Study Intervention	29
7.4 Evaluation at Completion of Study Intervention	30
7.5 Post-intervention Follow-up Period.....	31
7.6 Methods for Clinical Procedures	31
8. CRITERIA FOR EVALUATION AND ENDPOINT DEFINITION.....	31
8.1 Primary Endpoint.....	31
8.2 Secondary Endpoints	32
8.3 Exploratory Endpoint.....	35
8.4 Off-Agent Criteria	35
8.5 Off-Study Criteria.....	36

8.6	Study Termination	36
9.	CORRELATIVE/SPECIAL STUDIES	36
9.1	Rationale for Methodology Selection	36
9.2	Comparable Methods.....	37
10.	SPECIMEN MANAGEMENT	37
10.1	Laboratories	37

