2.3 Rationale

The goal of this Phase 1b window trial is to ensure that 9cUAB30 produces a biological effect in humans and to identify candidate RXR signaling pathways that may play a role for cancer prevention. We believe the low toxicity of the rexinoid 9cUAB30 will be well-received for prevention of breast cancers in the high risk population, and potentially even better received for women who have had cancer and wish to prevent the occurrence of a second tumor. The results of this study will help to determine the suitability of continued study with 9cUAB30 as a chemoprevention drug in trials proposed by the NCI DCP in the Clinical Development Plan of 9cUAB30.

Treatment with 9cUAB30 in animal models reduced proliferation and number of tumors in both ER+ and ER- breast cancer animal models, suggesting a chemopreventive effect of the drug. To evaluate the anti-proliferative effect in humans, we chose the pre-surgical window trial design. The model of short-term administration of a drug between the window of diagnosis to operative intervention, allows for evaluation of biomarker response from baseline (core biopsy) to post-treatment (surgery). Several pre-surgical trials

have shown the ability of SERMs to reduce proliferation as measured by Ki67 after short-term administration. In these trials administration of tamoxifen or other SERM results in decrease of Ki67 by approximately 40% when surgical resection samples are compared with pretreatment core biopsy samples.³²⁻³⁵ We expect that 9cUAB30 will reduce proliferation and increase apoptosis.

Because breast cancer prevention/therapy preclinical mouse model data with Targretin, 9cRA and 9cUAB30 suggest a linear relationship between increasing dose/concentration and anti-cancer effects, it is important to explore the highest 9cUAB30 dose that pharmacodynamics suggest. The new formulation of 9cUAB30 will significantly lower the gelatin: active ingredient ratio (12 capsules vs 3 capsules) thus raising the potential of higher tissue exposure at 240 mg as compared to 160 mg. Therefore, we plan to “pilot” the 240 mg dose in initial participants with planned assessment of C_{2hr} (Tmax usually at 2 hours) at 2 hours post initial dose. If real time assessment of 9cUAB30 concentrations observe a significant increase over 957 ng/ml levels we will continue at 240 mg/day. If initial concentrations are not appreciably >957 ng/ml with 240 mg/day, participants will be treated at 160 mg/day.

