3. SUMMARY OF STUDY PLAN

Eligible participants will be \geq 18 years of age and newly diagnosed pre- or post-menopausal patients with core biopsy proven invasive breast cancer between 0.5 cm and 5 cm in size or DCIS that is \geq 1.0 cm in size and is either Grade 3 ER+ DCIS or ER- DCIS of any grade

Patients agreeing to participate will take 9cUAB30 240 mg (160 mg contingent on interim analysis) by mouth daily for 14 – 28 days until the time of surgery. Tissue from the core biopsy will be used for the pre-treatment biomarker analysis. The tissue obtained from the surgical excision will be used for post-treatment biomarker analysis. We plan to enroll ER+ participants and ER- participants for a total of up to 41 participants undergoing intervention. We expect the study to be complete within 18-24 months. Beginning in November 2021, participants will be limited only to estrogen receptor negative status.

At baseline all participants will have a complete medical history, physical examination and review of concomitant medications. Participants will undergo laboratory testing to determine eligibility within 30 days prior to day 1 of the study. Baseline laboratory tests will include WBC, differential, hemoglobin,

hematocrit, platelets, INR, PTT, AST, ALT, total bilirubin, alkaline phosphatase, BUN, creatinine, calcium, glucose, albumin, electrolytes (Na, K, Co₂, Cl), HDL, LDL, total cholesterol, triglycerides, thyroid stimulating hormone, FT₃, and FT₄ (may omit any if collected as part of initial cancer workup documented in the medical record within 30 days of study Day 1). A plasma and urine sample for pharmacokinetic (PK) analysis will also be obtained. An additional 30 ml blood sample will be obtained to evaluate and measure the immune response of 9cUAB30 in participants 6-25.

For the first 5 participants, two extra plasma PK samples will be collected after administering the first dose of the study agent at 5 minutes and 2 hours post the drug administration to evaluate the C_{max}. After the first 5 participants complete study participation, their PK samples will be evaluated to determine the C_{max} and adverse events will be evaluated to determine safety of the 240mg dose. Based on this evaluation, it will be determined to continue study dose at 240mg or to reduce to 160mg (refer to section 13.9).

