Surgery must occur between Days 15 and 29 of the study. On the day of surgery or the day before surgery laboratory tests will be obtained and include WBC, differential, hemoglobin, hematocrit, platelets, INR, PTT, AST, ALT, total bilirubin, alkaline phosphatase, BUN, creatinine, calcium, glucose, albumin, electrolytes (Na, K, Co₂, Cl), HDL, LDL, total cholesterol, triglycerides, thyroid stimulating hormone, FT₃, FT₄, as well as a plasma and urine sample for PK. The history and physical examination will be obtained and/or updated within 24 hours of the procedure. An additional 30 ml blood sample will be obtained during this visit to evaluate and measure the immune response of 9cUAB30 by comparing it to the sample obtained at baseline for participants 6-25.

At the time of surgery, tissue samples will be obtained of remnant tumor and processed as is the usual standard at each institution. One H&E stained slide, 5 unstained slides of 5 μ m thickness and 5 unstained

slides of 10 μ m thickness will be requested from the formalin fixed paraffin embedded (FFPE) tissue blocks containing tumor as described in section 10.2.1

The plasma and urine samples for PK will be sent to University of Wisconsin - CP lab for evaluation. The immunogenicity samples will be sent to University of Washington – Tumor Vaccine Group. All other baseline and pre-surgical laboratory studies will be performed at each participating institution.

All participants will receive \$30 for completing the screening visit, \$70 for completing the surgery visit and returning the blood pressure machine as compensation towards the extra efforts taken such as travel expenses, parking, time missed from work or other expenses associated with the study visits. The first 5 participants will be given additional \$50 for the additional time required for the study visit.

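### The interim dose-reduction trigger counts only grade 2 hypertriglyceridemia, so two grade 3 cases, or one grade 2 and one grade 3, do not meet it as written

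*Combined protocol and SAP*

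**What the plan says.** Section 13.9 sets one look at the dose: "There will be an interim analysis after first 5 participants complete the study at dose 240 mg". Two criteria lead to 160 mg. The first is a mean Cmax that does not exceed 957 ng/mL. The second is that two or more "subjects experience grade 2 hypertriglyceridemia of any attribution". The Schema footnote gives the same lipid rule: "subjects experience grade 2 hypertriglyceridemia of any attribution then the study dose will be changed to 160mg". In both places the at-least sign applies to the number of participants, not to the grade.

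The only other graded study-level rule is also in Section 13.9: "If any subjects experience grade 4 or higher toxicity, the study will be suspended for accrual". Section 5.6 permits a lower study dose when the 13.9 rules are met, and then says: "No other dose modifications will be allowed". Section 3 says of the first five participants that "adverse events will be evaluated to determine safety of the 240mg dose", and refers to Section 13.9 for the decision.

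**The concern.** CTCAE v4.0 (Section 11.1.3) treats grades 2 and 3 as separate categories, so a rule that names only grade 2 does not count a grade 3 case. The plan marks thresholds where it means them: Section 13.9 says that grade 4 and above suspends accrual, and Section 2.2.4 uses an at-least sign with grade 2. A bare grade 2 therefore cannot be taken as the document's shorthand for grade 2 and above. No study-level rule names grade 3.

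At stake is whether later participants stay on 240 mg after a lipid signal worse than the one meant to lower the dose. Hypertriglyceridemia is the only toxicity singled out for dose reduction, and Section 2.2 describes hyperlipidemia, including raised triglycerides, as dose-limiting for the best-studied rexinoid.

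**Working it through.** **The plan's own figure.** The only operating characteristic given for this look is the power of the Cmax test in Section 13.1, 0.69. With n = 5, a difference of 1668 − 957 = 711 and SD 611, the effect size is 711/611 = 1.164 and the noncentrality is 1.164 × √5 = 2.602. The one-sided 5% critical value on 4 degrees of freedom is 2.132, and the noncentral t gives power 0.689. The figure reproduces. No operating characteristic is given for the lipid rule.

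**The rule applied to each pattern.** With two affected participants at grade 2 or 3:

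| Grades | Count as written | Trigger as written | Trigger with grade 2 or higher |
|---|---|---|---|
| 2 and 2 | 2 | met | met |
| 2 and 3 | 1 | not met | met |
| 3 and 3 | 0 | not met | met |

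Across all five participants, eight combinations of (grade 2, grade 3) counts have two or more affected and still miss: (0,2), (0,3), (0,4), (0,5), (1,1), (1,2), (1,3) and (1,4).

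**Could a grade 3 participant also be counted at grade 2?** Normally not. After screening, the lipid panel is scheduled once: "On the day of surgery or the day before surgery laboratory tests will be obtained" (Section 3; Section 7.1 agrees). Section 7.3.3 allows an extra site evaluation for a reported event, but no second on-treatment triglyceride draw is planned.

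**How often it could matter (illustration).** Inputs:
- n = 5 (Section 13.9).
- Rate *p* of grade 2 or higher, assumed to be 5% to 16.7%. The upper value is the any-grade rate on active doses in Table 3: (2+2+2+1+0)/(8+9+8+9+8) = 7/42. Placebo was 2/12, also 16.7%.
- Share *s* of those cases at grade 3, assumed to be 10% to 50%. The documents do not give hypertriglyceridemia by grade for the multi-dose study.

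The probability of at least two among five is T(x) = 1 − (1−x)⁵ − 5x(1−x)⁴. The corrected rule uses x = *p*. The literal rule uses x = *p*(1−*s*).

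| *p* | *s* | Corrected | Literal | Shortfall (points) |
|---|---|---|---|---|
| 5% | 10% | 2.3% | 1.8% | 0.4 |
| 5% | 50% | 2.3% | 0.6% | 1.7 |
| 16.7% | 10% | 19.6% | 16.5% | 3.1 |
| 16.7% | 3/7 | 19.6% | 7.5% | 12.2 |
| 16.7% | 50% | 19.6% | 5.9% | 13.8 |

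Shortfalls are taken from unrounded values. The 3/7 row is explained under the objection.

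**What the 240 mg data exclude.** Table 3 shows hypertriglyceridemia in 0 of 8 at 240 mg. The one-sided 95% upper bound on the any-grade rate is 1 − 0.05^(1/8) = 31%. Those eight took the 12-capsule form (Section 2.2.4). Section 2.3 describes the 3-capsule form as lowering the gelatin ratio, "thus raising the potential of higher tissue exposure at 240 mg as compared to 160 mg".

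**The case against.** The strongest reply is that nobody would apply the rule literally. A toxicity trigger is ordinarily read as a minimum, and a team holding two grade 3 results is unlikely to decide that they are too severe to count. Review also goes beyond a bare count: adverse events in the first five are evaluated, the data monitoring committee follows safety, and the sponsor may stop the study at any time (Section 8.6). This stands as a limit on the consequence. It does not change the text: Section 3 refers back to 13.9, and Section 5.6 ties any reduction to the 13.9 rules.

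Second, exposure is narrow. The rule runs once, after the first five have finished, so it protects only later participants, who are dosed for 14 to 28 days and enter with triglycerides at or below 1.5 times the upper limit. In Version 20, dated January 2022, the look may already be past. The documents do not say, and the current text still states the rule prospectively.

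Third, the top of the illustrated range is generous. Section 6.2 says that typical retinoid and rexinoid toxicities, hyperlipidemia among them, were neither frequent nor of significant grade. In Table 2 the extracted row labels are displaced; taking the footnoted last row as grade 3, nobody at 40 or 80 mg had a grade 3 event of any kind. Four of the seven hypertriglyceridemia cases were at those doses, so at most 3 of 7 could have been grade 3. That cap lowers the largest shortfall from 13.8 to 12.2 points, still with every event treated as grade 2 or higher. This stands, but it trims only the illustration; the defect needs no assumed rate.

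**Conclusion.** The concern holds. As written, 3+3 and 2+3 miss a trigger that 2+2 meets, and nothing elsewhere in the plan corrects it. It is a minor wording error, worth correcting because it sits in a pre-specified safety threshold and reverses the order of severity.

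The practical effect is probably small. The shortfall in trigger probability is 0.4 to 1.7 points at an assumed 5% rate. At 16.7% it is at most 12 to 14 points, which requires treating every any-grade event as grade 2 or higher and close to half of them as grade 3. Both the rates and the grade 3 share are assumptions. The 0 of 8 at 240 mg is reassuring but leaves rates up to 31% open, and it comes from a formulation replaced partly in the hope of higher exposure.

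**What to change.** In Section 13.9, criterion 2, and in the Schema footnote, insert *or higher* after *grade 2*, so that the dose is reduced when at least two participants have hypertriglyceridemia of grade 2 or higher, whatever its attribution. This also settles mixed grades. Leave the grade 4 rule as it is; a grade 4 case then counts toward dose reduction and also suspends accrual.

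If the look has already taken place, correct the text and record how grade 3 values were counted.

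The cost is two words in two places, with no change to sample size, schedule or analysis.
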